#### 12.5 Pharmacogenetics analysis plan

This analysis will be performed at the end of the trial by Gateway Biotechnology. To identify genetic variants with ZNS protection against hearing loss, we will first use univariate logistic regression analyses to identify potential confounding variables: sex, age, Z-scores of drug concentration, Z-scores of noise intensity and duration, and Z-scores of hearing functions measure immediately following surgery. Single-marker allelic association analyses will be conducted on the two imputed data sets in PLINK v1.07. The data will be analyzed with a logistic regression model on the additive continuous dosage of minor alleles from 0 to 2 to account for uncertainty of imputation. We will combine association results in the two cohorts by performing a genome-wide inverse-variance weighting metaanalysis using PLINK v1.07, and assuming a fixed-effect model. Functional annotation of top-associated markers will be performed with R package NCBI2R 1.4.6 (http://CRAN.Rproject. org/package=NCBI2R), and key regional association plots of meta-analyzed results will be generated. To confirm whether these variants are specific to ZNS response, we will apply CEP SKAT to analyze genetic associations based on Z-scores of audiogram average threshold shifts and DPOAE amplitudes. All genetic variants, including both common and rare variants, will be included in this association study. Age, gender, and noise duration and intensity will be adjusted for the analysis. The analysis will also be performed using hearing data collected two weeks following surgery. The only differences will be a) using the Z scores of ECochG AP amplitude, latency, and width as well as WIN score, and b) using average audiogram threshold shifts and DPOAE amplitudes at 30 days post-treatment. We will also include metabolite profiling data to support potential genotypic responses to drug treatments. To control for confounding effects, these models will be adjusted for age, gender, and noise duration and intensity. Finally, the control and ZNS-treated comparisons will be performed using post-hoc comparisons with a Bonferroni adjustment for multiple comparisons of any ZNS versus none. Statistical analyses will be performed using the CEP-SKAT method in R language, and the statistical software SAS version 9.4 for Windows will be used for additional analysis.

## **APPENDIX A: Definitions for Adverse Event Reporting**

### A. Adverse Events (AEs)

As defined in 21 CFR 312.32:

**Definition:** any untoward medical occurrence associated with the use of a drug in humans, whether or not considered drug-related.

**Grading:** the descriptions and grading scales that should be used are those provided by the Department of Health and Human Services' Office for Human Research Protections (OHRP). A copy of this guidance can be found on OHRP's website: http://www.hhs.gov/ohrp/policy/advevntguid.html

**Attribution (relatedness), Expectedness, and Seriousness:** the definitions for the terms listed that should be used are those provided by the Department of Health and Human Services' Office for Human Research Protections (OHRP). A copy of this guidance can be found on OHRP's website:

http://www.hhs.gov/ohrp/policy/advevntguid.html

### **B.** Suspected Adverse Reaction (SAR)

As defined in 21 CFR 312.32:

**Definition:** any adverse event for which there is a reasonable possibility that the drug caused the adverse event. "Reasonable possibility" means there is evidence to suggest a causal relationship between the drug and the adverse event. "Suspected adverse reaction" implies a lesser degree of certainty about causality than adverse reaction, which means any adverse event caused by a drug.

### C. Life-Threatening Adverse Event / Life Threatening Suspected Adverse Reaction

As defined in 21 CFR 312.32:

**Definition:** any adverse drug event or suspected adverse reaction is considered "life-threatening" if, in the view of the investigator, its occurrence places the patient at immediate risk of death. It does not include an adverse event or suspected adverse reaction that, had it occurred in a more severe form, might have caused death.

### D. Serious Adverse Event (SAE) or Serious Suspected Adverse Reaction

As defined in 21 CFR 312.32:

**Definition:** an adverse event or suspected adverse reaction is considered "serious" if, in the view of the investigator, it results in any of the following outcomes:

o Death

- o A life-threatening adverse event
- o Inpatient hospitalization or prolongation of existing hospitalization
- A persistent or significant incapacity or substantial disruption of the ability to conduct normal life functions
- o A congenital anomaly/birth defect
- Any other important medical event that does not fit the criteria above but, based upon appropriate medical judgment, may jeopardize the subject and may require medical or surgical intervention to prevent one of the outcomes listed above

## E. Protocol Exceptions

**Definition:** A planned change in the conduct of the research for one participant.

#### F. Deviation

**Definition:** Any alteration or modification to the IRB-approved research without prospective IRB approval. The term "research" encompasses all IRB-approved materials and documents including the detailed protocol, IRB application, consent form, recruitment materials, questionnaires/data collection forms, and any other information relating to the research study.

A minor or administrative deviation is one that does not have the potential to negatively impact the rights, safety, or welfare of participants or others or the scientific validity of the study.

A major deviation is one that does have the potential to negatively impact the rights, safety, or welfare of participants or others or the scientific validity of the study.

## **APPENDIX B: Reporting Timelines**

Event	HRPO	FDA
Serious AND unexpected suspected adverse		Report no later than 15 calendar days after it is
reaction		determined that the information qualifies for reporting
Unexpected fatal or life-threatening		Report no later than 7 calendar days after initial
suspected adverse reaction		receipt of the information
Unanticipated problem involving risk to	Report within 10 working days. If the event results in	
participants or others	the death of a participant enrolled at WU/BJH/SLCH,	
	report within 1 working day.	
Major deviation	Report within 10 working days. If the event results in	
	the death of a participant enrolled at WU/BJH/SLCH,	
	report within 1 working day.	
A series of minor deviations that are being	Report within 10 working days.	
reported as a continuing noncompliance		
Protocol exception	Approval must be obtained prior to implementing the	
	change	
Clinically important increase in the rate of a		Report no later than 15 calendar days after it is
serious suspected adverse reaction of that list		determined that the information qualifies for reporting
in the protocol or IB		
Complaints	If the complaint reveals an unanticipated problem	
	involving risks to participants or others OR	
	noncompliance, report within 10 working days. If the	
	event results in the death of a participant enrolled at	
	WU/BJH/SLCH, report within 1 working day.	
	Otherwise, report at the time of continuing review.	
Breach of confidentiality	Within 10 working days.	
Incarceration	If withdrawing the participant poses a safety issue,	
	report within 10 working days.	
	If withdrawing the participant does not represent a	
	safety issue and the patient will be withdrawn, report at	
	continuing review.	

Event	HRPO	FDA
Adverse event or SAE that does not require	If they do not meet the definition of an unanticipated	The most current toxicity table from the DSM report
expedited reporting	problem involving risks to participants or others, report	is provided to the FDA with the IND's annual report.
	summary information at the time of continuing review	
Minor deviation	Report summary information at the time of continuing	
	review.	
Complaints	If the complaint reveals an unanticipated problem	
	involving risks to participants or others OR	
	noncompliance, report within 10 working days. If the	
	event results in the death of a participant enrolled at	
	WU/BJH/SLCH, report within 1 working day.	
	Otherwise, report at the time of continuing review.	
Incarceration	If withdrawing the participant poses a safety issue,	
	report within 10 working days.	
	If withdrawing the participant does not represent a	
	safety issue and the patient will be withdrawn, report at	
	continuing review.	

Event	WU (Coordinating Center)	Local IRB	FDA
Serious AND unexpected suspected	Report no later than 11 calendar days after it is	Report all applicable	The research team at Washington
adverse reaction	determined that the information qualifies for	events to local IRB	University is responsible for reporting all
	reporting.	according to local	applicable events to the FDA as needed.
Unexpected fatal or life-threatening	Report no later than 4 calendar days after initial	institutional	
suspected adverse reaction	receipt of the information.	guidelines.	
Unanticipated problem involving	Report no later than 4 calendar days after initial		
risk to participants or others	receipt of the information.		
Adverse event or SAE that does not	As per routine data entry expectations		
require expedited reporting	_ · · · ·		
Protocol exception	Approval must be obtained prior to implementing the		
	change.		

## **APPENDIX C: Washington University Unanticipated Problem Reporting Cover Sheet**

## **SAE COVER SHEET- Secondary Site Assessment**

Washington University HRPO#:	Sponsor-Investigator:
Subject Initials:	Subject ID:
Treating MD:	Treating Site:
EVENT TERM:	Admission Date:
EVENT GRADE:	Date of site's first notification:

Treating WID Event Assess	iment:	
Is this event possibly , prob	ably, or definitely related study treatme	ent?
yes	no	
If yes, please list wh	ich drug (if more than one)	
Explain		
Physician's Name	Physician's Signature	Date

Page 48 of 55 Version: 03 March 2023

## **APPENDIX D: Questionnaire 1a: Hearing History and Occupation Exposure – Visit 1**

## **Hearing History and Occupation Exposure** Visit 1

1. In the ear opposite of sur	gery, do you have any diff	iculties hearing speech?
□ No □	Yes, sometimes	□ Yes, often
2. In the ear opposite of sur sounds?	gery, do you have any diff	ciculties hearing other types of
□ No	Yes, sometimes	□ Yes, often
3. Do you have tinnitus, rin If yes, A. Which ear? □ R	ight □ Left	
	nitus start?	
1. Suddenly o	or gradually?	
4. Have you worked in any □ Yes □ No	of the following types of	loud-noise occupations?
Circle all that apply, even if	very brief:	
Logging/lumber industry	Mining	Farming
Factory	Landscape (lawnmower/weedeater/chain	Printing asaw)
Truck Driver	Pilot	Police
Construction	Military	Hunting (gun powder)
Fire Department	Musician/Theatrical performer	
Current Occupation:		

Version: 03 March 2023 Page 49 of 55

-	o loud noise during recreational or leisure-time activities boat engines, auto engines, motorcycle, ski-mobile, or loud
□ Yes □ No	
If yes, describe:	
6. Have you undergone any	accidental exposure to sudden, intense noise?
□ Yes □ No	
If yes, 6a. Please explain: ty	rpe of noise
6b. Which ear or side	of your head was exposed?
6c. Your age at the tir	me of noise exposure
	elatives who have, or have had, any problems with their No
If yes, please indicate	the nature of their problem(s), and their relationship to you.
8. Do you have any blood r  ☐ Yes ☐ No	elatives who have, or have had, tinnitus?
If yes, please indicate th	e nature of their problem(s), and their relationship to you.
REVIEWED BY	
CRC signature	Date
PI Signature	Date

Version: 03 March 2023 Page 50 of 55

# APPENDIX E: Questionnaire 1b: Hearing History and Occupation Exposure – Visit 3 Hearing History and Occupation Exposure Visit 3

1. In the ear opposite of surg	gery, do you have any dif	fficulties hearing speech?
□No□	Yes, sometimes	□ Yes, often
2. In the ear opposite of surg sounds?	gery, do you have any dif	fficulties hearing other types of
□ No Y	es, sometimes	□ Yes, often
3. Do you have tinnitus, ring If yes, C. Which ear? □ Ri		□ No
D. When did the tinn	itus start?	
2. Suddenly o	r gradually?	
4. Since your surgery, have situations?  ☐ Yes ☐ No	you been in any of the fo	ollowing types of loud-noise
Circle all that apply, even if	very brief:	
Logging/lumber industry	Mining	Farming
Factory	Landscape (lawnmower/weedeater/chai	Printing
Truck Driver	Pilot	Police
Construction	Military	Hunting (gun powder)
Fire Department	Musician/Theatrical performer	Rock Concerts

Version: 03 March 2023 Page 51 of 55

Pharmaceutical Interventions for Noise-Induced Hearing Loss—Acute Exposure Treatment (PINIHL-AET)

Woodworking Listening to music on MP3 players

leisure-time activ		osed to loud noise during recreational or er tools, boat engines, auto engines,
□ Yes	□No	
If yes, describe: _		
6. Since your sur intense noise?	gery, have you undergo	ne any accidental exposure to sudden,
□ Yes	□No	
If yes, Plea	se explain: type of noise	
Which ear	or side of your head was	s exposed?
REVIEWED BY		
CRC signature		Date
PI Signature		Date

Version: 03 March 2023 Page 52 of 55

## APPENDIX F: LENS-Q Adapted for Surgical Noise Study –Visit 1

**LENS-Q Adapted for Surgical Noise Study:** The point of this modified survey is to stratify participants into relatively higher and relatively lower exposure groups.

## **Noise Exposure History Interview Questions**

1.

- A. In your occupation, how often are you exposed to loud noise(s) where you have to shout to be heard? (For example, loud equipment or trucks, loud ship or jet engines, exposure from the rifle range, sirens, K-9 noise, loud crowds, loud music (e.g. concert/band events), loud noise from construction sites)
  - a. Daily
  - b. Less than daily/more than weekly
  - c. Weekly
  - d. Less than weekly/more than monthly
  - e. Monthly
  - f. Less than monthly/more than yearly
  - g. Yearly
  - h. Less than yearly
  - i. Never
- B. How likely are you to be wearing hearing protection when this occurs (circle one)?

	Never	Rarely	Sometimes	Usually	Always	
C. How r	nany years h	ave you work	ted in your occup	atıon'?		

- 2. Have you served in the military? If yes:
  - A. How often did your **military service** cause you to be exposed to loud noise(s) where you had to shout to be heard? (For example, loud equipment or trucks, loud ship or jet engines, loud aircraft)
    - a. Daily
    - b. Less than daily/more than weekly
    - c. Weekly
    - d. Less than weekly/more than monthly
    - e. Monthly
    - f. Less than monthly/more than yearly
    - g. Yearly
    - h. Less than yearly
    - i. Never

Version: 03 March 2023 Page 53 of 55

	. Hov	v likely were yo	ou to be wear	ring hearing prote	ction when thi	s occurred (circle one)?	
		Never	Rarely	Sometimes	Usually	Always	
C.	. Hov	w many years d	id you serve	in the military? _			
		w often did or dould have to sho			e you to be ex	posed to loud noise(s) where	
	a.	Daily					
	b.	Less than dail	y/more than	weekly			
	c.	Weekly					
	d.	Less than wee	kly/more tha	n monthly			
	e.	Monthly					
	f.	Less than mor	nthly/more th	an yearly			
	g.	Yearly					
	h.	Less than year	rly				
	i.	Never					
		Never	Kareiy	Sometimes	Osuany	Always	
C.	. Hov	v many years w	ere you invo	lved with a recrea	ational activity	where you had to shout to be	,
		• •	•	lved with a recrea	•	where you had to shout to be	
he	eard?				-	·	2
he In A.	eard? eithe . Hov	er your occupat	ion, your mil	litary service, or y	your recreation	nal activities: or example, shooting range,	•
he In A.	eard? eithe . How rget p	er your occupat	ion, your mil	litary service, or y	your recreation	nal activities: or example, shooting range,	3
he In A.	eard? eithe . How rget p	er your occupat w often have yo oractice, huntin	ion, your mil ou been expos g, explosions	litary service, or y sed to sudden inte s, cannon fire, gur	your recreation	nal activities: or example, shooting range,	
he In A.	eithe eithe . How rget p a. b.	er your occupat w often have yo oractice, huntin Daily	ion, your mil ou been expos g, explosions	litary service, or y sed to sudden inte s, cannon fire, gur	your recreation	nal activities: or example, shooting range,	
he In A.	eithe eithe . How rget p a. b.	er your occupat w often have your practice, huntin Daily Less than dail Weekly	ion, your miles been exposed g, explosions	litary service, or y sed to sudden inte s, cannon fire, gur weekly	your recreation	nal activities: or example, shooting range,	
he In A.	eard? eithe . How rget p a. b.	er your occupat w often have your practice, huntin Daily Less than dail Weekly	ion, your miles been exposed g, explosions	litary service, or y sed to sudden inte s, cannon fire, gur weekly	your recreation	nal activities: or example, shooting range,	
he In A.	eithe Hoverget pa. b. c.	er your occupate woften have your oractice, huntin Daily Less than dail Weekly Less than wee	ion, your miles been exposed g, explosions y/more than ekly/more that	litary service, or y sed to sudden inte s, cannon fire, gur weekly un monthly	your recreation	nal activities: or example, shooting range,	
he In A.	eithe Hoverget parts b. c. d.	er your occupate woften have your oractice, huntin Daily Less than dail Weekly Less than weekly Monthly	ion, your miles been exposed g, explosions y/more than ekly/more that	litary service, or y sed to sudden inte s, cannon fire, gur weekly un monthly	your recreation	nal activities: or example, shooting range,	
he In A.	eithe Hoverget pa. b. c. d. e. f.	er your occupate woften have your occupate your occupate work of the practice, huntin Daily Less than dail Weekly Less than weekly Monthly Less than monthly	ion, your miles been exposed been explosions by/more than ekly/more than	litary service, or y sed to sudden inte s, cannon fire, gur weekly un monthly	your recreation	nal activities: or example, shooting range,	

Version: 03 March 2023 Page 54 of 55

B. Were you wearing hearing protection when this occurred (circle one)?

Never Rarely Sometimes Usually Always

## **Noise Exposure Group Assignment Based on Interview Questions**

- Participants with a response to 1.A., 2.A., or 4.A. of monthly or more frequent exposure are assigned to the higher noise group. Participants with less than monthly exposure are assigned to the lower noise group.
- Participants with a response to 1.C., 2.C, or 3.C. of 5 years or more are assigned to the Higher Noise group.

Version: 03 March 2023 Page 55 of 55

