2.4 Randomisation

Eligible subjects will be randomized in a balanced fashion into one of the 3 arms: ZNS 100 mg pre-op, Placebo, or ZNS 100 mg post-op. To balance noise-exposure history across study arms we will employ stratified randomization. The subjects will be stratified based on noise exposure survey responses (see table below), and will then be randomized to study groups. Randomization will be based on the randomization list generated by unblinded statistician using a computer algorithm written in SAS® using randomly selected blocks of sizes 3. Within each block of 3, there will be 1 subject assigned to each study group. The random assignment of subjects to the different study groups will be associated with consecutively assigned random numbers which will be unique for each study subject. The stratified kit list will be provided to Advanced Rx who will package and label the drug for shipment to the pharmacist. Each kit will contain two bottles and will be labeled with the same kit number. The bottle will not contain any information of the treatment allocation. One interim analysis is planned, once 33% (n=78) of the subjects have completed participation in the study.

Name	Description
1: High Noise	Screening: LENS-Q Adapted for Surgical Noise Study – 1A Or 2A Or 4A = a.Daily, Or b.Less than daily/more than weekly, Or c.Weekly, Or d.Less than weekly/more than monthly Or e.Monthly OR 1C Or 2C Or 3C >= 5 Years

Name	Description
2: Low Noise	Screening: LENS-Q Adapted for Surgical Noise Study – 1A AND 2A AND 4A = f.Less than monthly/more than yearly, g.Yearly, h.Less than yearly Or i.Never OR 1C AND 2C AND 3C < 5 Years

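### Five years in any occupation or in military service, quiet or noisy, is enough for the High Noise stratum, while the frequency of loud recreational noise (item 3A) is in no rule

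*Protocol*

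**What the plan says.** Appendix F states the purpose of the questionnaire: "The point of this modified survey is to stratify participants into relatively higher and relatively lower exposure groups". Protocol 5.2 and SAP 2.4 give balance of noise-exposure history across arms as the reason for stratifying.

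The assignment rules at the end of Appendix F are:

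- Frequency: "Participants with a response to 1.A., 2.A., or 4.A. of monthly or more frequent exposure are assigned to the higher noise group".
- Its counterpart: "Participants with less than monthly exposure are assigned to the lower noise group".
- Years: "Participants with a response to 1.C., 2.C, or 3.C. of 5 years or more are assigned to the Higher Noise group".

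The table in SAP 2.4 (and in Protocol 5.2) joins the frequency clause for High by OR to "1C Or 2C Or 3C >= 5 Years". The Low row also joins its two clauses by OR: less than monthly on 1A, 2A and 4A, or under 5 years on 1C, 2C and 3C.

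The items differ in what they measure. Item 1A is about noise: "In your occupation, how often are you exposed to loud noise(s) where you have to shout to be heard". Item 1C asks only for years worked in the occupation, and 2C only for years of military service. Item 3C is tied to noise, because it counts years in a recreational activity "where you had to shout to be" heard. Item 3A asks how often recreation brings shouting-level noise. Item 4A asks how often sudden intense noise occurred at work, in service or in recreation.

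A covariate for noise exposure history, split into high and low risk, enters the supportive logistic regression (Protocol 12.2.1, SAP 7.1.1) and the secondary ANCOVA (Protocol 12.2.2, SAP 7.1.2). Neither document defines it further.

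**The concern.** A stratification factor should separate patients on the thing to be balanced. Here one route into High requires no noise at all: someone with 20 years in a quiet office job who answers never to every noise question satisfies the years clause. In the other direction, someone with daily shouting-level recreational noise for 4 years, 3 years in a quiet job and no impulse noise satisfies neither High clause.

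Two things are at stake. The first is balance: the primary Fisher test does not adjust for noise history, so the design is its only guard against chance imbalance on that factor. The second is adjustment: if the undefined noise-history covariate is this stratum, the logistic and ANCOVA models adjust for a variable that partly records length of employment, which is likely to track age, and age is already in those models.

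**Working it through.** **1. What the years trigger adds.** High is met by monthly or more on 1A, 2A or 4A, or by 5 or more years on 1C, 2C or 3C. Anyone with monthly or more noise on those frequency items is High already. The only people whom 1C or 2C can move into High therefore have less than monthly noise on all three. This needs no assumption.

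**2. Where those people fall.** They also meet the first clause of the Low row, and the Appendix F sentence that sends less than monthly exposure to the lower group. In the operational table, a daily-exposed patient with under 5 years on 1C, 2C and 3C meets both rows too. No order of precedence is given.

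**3. The plan's own figure.** With 78 per arm, 50% versus 25% and one-sided alpha 0.0125, the stated power is 80.4%. The Walters arcsine approximation gives 80.41% and exact enumeration of Fisher's test gives 80.7%. The stratum enters neither calculation.

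**4. Size of the loss in balance, under the High-if-either reading.** Assumed inputs, not in the documents: q is the share with monthly or more noise on 1A/2A/4A, t is the share with 5 or more years on 1C/2C/3C, and the two are independent. From the documents: 78 per arm, blocks of 3 within stratum.

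- High share: H = q + (1 - q)t.
- Share of High there by years alone: 1 - q/H.
- SD of the between-arm difference in exposed share, unstratified: sqrt(2q(1 - q)/78).
- With strata (incomplete blocks ignored), only the within-stratum variance remains. Low contains no exposed patients, so this is H(q/H)(1 - q/H) = q(1 - q)t/H. The unstratified SD is thus multiplied by sqrt(t/H).

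For q = 0.2, t = 0.5: H = 0.2 + 0.8 × 0.5 = 0.60; by years alone 1 - 0.2/0.6 = 67%; unstratified sqrt(0.32/78) = 6.4 points; under the rule 6.4 × sqrt(0.5/0.6) = 5.8 points.

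| q | t | H | High by years alone | SD unstratified (points) | SD under rule (points) |
|---|---|---|---|---|---|
| 0.2 | 0.3 | 44% | 55% | 6.4 | 5.3 |
| 0.2 | 0.5 | 60% | 67% | 6.4 | 5.8 |
| 0.2 | 0.8 | 84% | 76% | 6.4 | 6.3 |
| 0.3 | 0.3 | 51% | 41% | 7.3 | 5.6 |
| 0.3 | 0.7 | 79% | 62% | 7.3 | 6.9 |
| 0.4 | 0.8 | 88% | 55% | 7.8 | 7.5 |
| 0.5 | 0.3 | 65% | 23% | 8.0 | 5.4 |
| 0.5 | 0.7 | 85% | 41% | 8.0 | 7.3 |

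Simulation (4,000 trials of 234 patients) agrees: 6.0 points at (0.2, 0.5), 5.6 at (0.3, 0.3), 6.7 at (0.3, 0.7) and 7.3 at (0.5, 0.7). The variance reduction runs from 13% at (0.2, 0.5) to 41% at (0.3, 0.3).

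**5. What the fix would give.** Suppose a share r = 10-20% (assumed) becomes High only through 3A or 3C. The same formula with r in place of t gives 3.4-5.0 points for q from 0.2 to 0.5; simulation gives about 3.4-5.1. Stratifying on 1A/2A/4A alone would give about 0.7 points, but that is automatic, because it stratifies on the very variable being scored, and it is not the proposed rule.

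**The case against.** The strongest reply is that High-if-either is itself an assumption. If frequency took precedence, the quiet-job patient would be Low and the tenure problem would vanish. That stands to this extent: as written, this patient's stratum is undefined, and it cannot be said that the plan makes the patient High. But rewriting Low as everyone not High, a natural repair of the overlap, would leave the years trigger in force.

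A reader might infer that the stratum mostly records job tenure and barely balances exposure. The documents do not support that as a general statement, because they give neither prevalence. It fits rows such as (0.2, 0.8), but at (0.5, 0.3) only 23% of High is there by years alone and the variance of the imbalance is roughly halved (t/H = 0.46). The score in the working also counts frequency only, although duration is a legitimate part of noise history.

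A reader might also infer that recreational noise is ignored. It is not: 4A covers sudden intense noise in recreation and 3C covers years of loud recreation. What is left out is 3A.

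Nor do the documents say that the high/low-risk covariate is the LENS-Q stratum. It is the only noise-history dichotomy they define, so the link is plausible but unstated.

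Finally, the effect on the primary result is small. If exposed patients had 20 points more PTS (an assumption), a 7-point imbalance would shift the arm difference by 0.20 × 7 = 1.4 points. The planned effect is 25 points and its sampling SD is sqrt(0.25/78 + 0.1875/78) = 7.5 points. Chance imbalance is already part of that error.

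**Conclusion.** The point holds as a flaw in a stated rule. Years in a quiet occupation or quiet service can trigger High, that trigger can only add people with less than monthly noise on 1A, 2A and 4A, and 3A is unused. The same people also qualify as Low with no tie-break.

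The stratum is weakened as a measure of noise history, by an amount that depends on prevalences outside the documents. With 20-50% exposed, 30-80% long tenure, independence and the High-if-either reading, the SD of the between-arm difference in exposed share is about 5-8 points, against 6-8 with no stratification.

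Randomisation and the unadjusted primary Fisher test remain valid, and the stated power is unaffected. It would be wrong to infer a biased primary result. The loss is in balance, and in the supportive logistic and secondary ANCOVA adjustment if their covariate is this stratum. This is an inexpensive improvement worth making, not a threat to the trial's main conclusion.

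**What to change.** In Appendix F, Protocol 5.2 and SAP 2.4:

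- Define High by monthly or more on any of 1A, 2A, 3A or 4A.
- Drop 1C and 2C as stand-alone triggers.
- State explicitly whether 3C of 5 years or more stays as a trigger. Keeping it admits rare but long-running noisy recreation, so it should be a deliberate choice.
- Define Low as everyone else, so that the strata are mutually exclusive.

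In SAP 7.1.1 and 7.1.2, state that the noise-history covariate is derived from the item-level LENS-Q answers by this rule. Keep the allocated stratum on record, and include it in the models or in a sensitivity analysis.

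The cost is wording and programming. No new data are needed: the items are already collected, and SAP Listing 16.2.5 lists the LENS-Q results. The downside is that patients already randomised were stratified under the old rule, so for some the covariate may differ from the allocated stratum. Updating the IRT for new patients is optional.
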